Study Design. This double-blind, randomized pilot clinical trial will prescreen an estimated 250 potential subjects, consent and further evaluate approximately 100 potential subjects, and ultimately enroll 70 subjects to ensure 40 subjects will provide a primary marijuana reduction outcome measure at four weeks post quit date. Subjects will be stratified by sex then randomized to one of two treatment groups (n=20 per drug group, 50% female): progesterone (PRO; 200mg 2x/day) or Placebo (PBO). They will take the medication for 5 weeks and will attend weekly clinic visits (see Visit Sequence & Procedure below for more information).

Setting: This project will be conducted at the Delaware Clinical Research Unit (DCRU). The DCRU has both inpatient and outpatient resources for the spectrum of biomedical research including special capabilities that were developed for study of substance use disorders. The Clinical and Translational Sciences Institute (CTSI), runs the DCRU and functions parallel to and supports the activities of the NIH funded CTSI, which it predicated. The DCRU includes: reception area, examination rooms, meeting rooms, clinical interview rooms, testing rooms for computer based performance tasks, a wet lab for handling bloods and other specimens, freezers (to -80°C), all essential staff offices, each with multiple telephone and computer lines through the University of Minnesota servers, locked limited access protocol, equipment and medication rooms, as well as secure cabinets for study files and essential supply and support areas and services.

Recruitment: To meet recruitment goals, we aim to enroll a total of 70 subjects (~6 subjects/month) to ensure a final sample size of 20 females and 20 males completing the study. Our primary recruitment method will be advertising in the mainstream media. While this type of recruitment can be challenging, our team has been successful with this form of recruitment. For example, our current study (PRO for smoking cessation) has had success with Facebook, Craigslist, TV, and radio advertising. Specifically, over the past seven months, we have received an estimated 300 phone calls from interested participants which resulted in the enrollment of 30 subjects (~8 subjects/month).

Study Sample. This study will enroll males (n=35) and females (n=35) who self-report use marijuana ≥4 days per week and are interested in changing their marijuana use. Specific eligibility criteria are as follows:

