| Marijuana: Since you last visit... (TPD - Times per day) | | MJ |
| Cigarettes: Since you last visit... (CPD) | | CPD |
| Caffeine: Since you last visit... (ozs.) | | CAFF |
| Computer Tasks: | | | | | | | | | |
| Immediate/Delayed Memory Task: Impulsivity & attention | | IMT DMT | | | | | | IMT DMT | |
| GoStop Computer Task: Response inhibition | | GoStop | | | | | | GoStop | |
| Balloon Analogue Risk Task: Risk-taking | | BART | | | | | | BART | |
| Biological Specimen Collection: | | | | | | | | | |
| Blood (plasma/serum): Hormones | BLOOD | | BLOOD | BLOOD | | BLOOD | | BLOOD | BLOOD |
| Urine: THC and Cotinine | | URINE |

Analysis Plan

Our primary outcome is change in marijuana use as defined by the TLFB at the week 4 visit relative to the baseline visit. This is a pilot study to generate data to potentially motivate and justify a future fully-powered study of PRO and marijuana cessation, so the intent of these analyses is to estimate magnitude and direction of treatment effects and associations with impulsivity (sex-specific and overall). While we expect baseline covariates to be balanced across treatment groups due to the randomization, this pilot study is small so both unadjusted and adjusted assessments of effects will be carried out by including the randomized treatment assignment and pre-specified adjusting covariates such as age, baseline progesterone, estradiol, baseline

impulsivity measures, etc. This pre-specified list will be determined by the study team during the finalization of the protocol, prior to the first study enrollment. We expect these analyses to be somewhat conservative, since they do not explicitly account for the randomized permuted blocking (Matts and Lachin, 1988). An analysis that accounts for the blocking (such as a stratified Mantel-Haenzel test) cannot be generalized to include the adjustment for impulsivity measures, for example, which are a focus of this proposal. All persons randomized and with a measured primary outcome at the week 4 visit will be included in this analysis, regardless of whether or not they ever took any of their assigned treatment (intent-to-treat analysis); persons with missed visits are discussed below.

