Addressing Hypothesis 1a: An unadjusted assessment of the treatment effect will come from a linear model of percent reduction in marijuana use on randomized treatment assignment, separately by sex. **Hypothesis 1b:** A linear model including both males and females will be used to estimate the overall gender effect on percent reduction in marijuana use. **Hypothesis 1c:** A linear model including both males and females will be used to estimate the association of serum progesterone with percent reduction in marijuana use; we will separately consider baseline progesterone, cumulative progesterone (summed over weeks 0-4), and week 4 progesterone.

Addressing Hypothesis 2a: A linear model including both males and females will be used to estimate the association of impulsivity with percent reduction in marijuana use. **Hypothesis 2b:** A linear model including both males and females will be used to estimate the interaction between baseline impulsivity and baseline serum progesterone on percent reduction in marijuana use.

Missing data plan: Quality assurance plans are described below. The primary outcome analysis will be carried out using two parallel models: one model will exclude subjects for whom we were unable to obtain a week 4 TLFB or urine THC. Since 'missing at random' is a strong statistical assumption to make, we will also carry out a parallel model that uses multiple imputation of the week 4 TLFB and urine THC based on an individual's previous visits' TLFB and urine THC levels. We will also examine whether persons missing their week 4 visit differed in their baseline characteristics or treatment assignment from persons not missing their week 4 visit.

Power: This is a pilot study to generate data to potentially motivate and justify a future fully-powered study of PRO and marijuana use. This study will estimate magnitude and direction of treatment effects and associations with impulsivity (sex-specific and overall). Hence, no power calculations are provided.

Data Safety and Monitoring Plan, Board, and Administration.

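### The analysis labelled intent-to-treat is an observed-outcome analysis by assigned arm, and up to four treatment estimates within each sex compete with none named as the lead.

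*Combined protocol and SAP*

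**What the plan says.** The Analysis Plan defines the analysis set in one sentence. It begins "All persons randomized and with a measured primary outcome at the week 4 visit will be included in this analysis", adds that inclusion does not depend on having taken treatment, and closes with "intent-to-treat analysis); persons with missed visits are discussed below".

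The missing data plan says "The primary outcome analysis will be carried out using two parallel models". In the first, "one model will exclude subjects for whom we were unable to obtain a week 4 TLFB or urine THC". The second is a "parallel model that uses multiple imputation of the week 4 TLFB and urine THC", based on each person's earlier TLFB and THC values. The plan will also check whether people missing Week 4 differ in baseline characteristics or assigned arm.

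On adjustment, "both unadjusted and adjusted assessments of effects will be carried out". The covariates are given as examples with an open end, and "This pre-specified list will be determined by the study team during the finalization of the protocol". Hypothesis 1a is written as an unadjusted linear model fitted separately by sex. The Power paragraph promises both sex-specific and overall effects and gives no power calculation.

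On numbers, Study Design says the trial will "ultimately enroll 70 subjects to ensure 40 subjects will provide a primary marijuana reduction outcome measure".

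**The concern.** Intent-to-treat has two parts: people are analysed in the arm they were assigned to, and everyone randomized is kept. The set described meets the first part only. Its estimate has the protection of randomization only if loss is unrelated to outcome, or relates to outcome in the same way in both arms. A reader who trusts the label would not think to ask.

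The second problem is the missing lead. The trial exists to estimate the size and direction of a treatment effect for a future study. If several versions of that effect are produced with equal standing, the one carried forward can be chosen after the results are seen. Nothing in the plan says what is concluded if the versions disagree.

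**Working it through.** **1. Size of the gap between enrolled and analysed.** Study Design gives 70 enrolled and 40 with the outcome: 70 − 40 = 30, and 30/70 = 42.9%. No dropout rate is stated, so the 70 cannot be reproduced independently. Randomization happens at the Baseline Visit, after screening. Study Adherence replaces people who attend nothing after screening but does not replace those who leave after randomization. If x of the 30 are lost before randomization, the share of randomized people left out is (30 − x)/(70 − x):

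| x | left out / randomized | share |
|---|---|---|
| 0 | 30/70 | 42.9% |
| 10 | 20/60 | 33.3% |
| 20 | 10/50 | 20.0% |
| 30 | 0/40 | 0% |

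The documents do not give x, so 43% is the upper end.

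**2. Number of competing estimates.** Two missing-data models × two adjustment versions = 4 within each sex. If the promised overall effect is also fitted, it has four versions too.

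**3. How far the four can differ.** A simulation with no treatment effect used assumed inputs: 35 per sex, 15 missing at random, four covariates, an outcome correlated about 0.7 with the prior visit, 10 imputations and 4,000 replicates. Within a sex, the largest and smallest of the four estimates differed by a median of 0.37 units and a 90th percentile of 0.72. The simulated outcome variance was 0.09 + 0.49 + 0.51 = 1.09 (SD 1.04), so these are about 0.35 and 0.69 SD. For comparison, the standard error with 10 per arm within a sex (20 per drug group, half female) is √(1/10 + 1/10) = 0.45 SD.

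**4. What outcome-related loss does to the observed-outcome estimate.** Assume 4/7 retained, with loss related to outcome in the progesterone arm only and a correlation c of 0.3 to 0.5 between staying and outcome. The shift is c·φ(z)/(4/7) with z = −0.18. That is c × 0.3925/0.5714 = 0.687c, or 0.21 to 0.34 SD.

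**5. What imputation does to the same bias.** Assume three earlier visits, equal correlation ρ between visits, and arm in the imputation model. In large samples the remaining bias is 0.687c(1 − R²), with R² = 3ρ²/(1 + 2ρ).
- ρ = 0.4: R² = 0.267, leaving 0.15 to 0.25 SD.
- ρ = 0.7: R² = 0.613, leaving 0.08 to 0.13 SD.

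**6. What happens if arm is left out.** The missing data plan lists only earlier TLFB and THC as predictors. Assume loss at random and a true effect building 0.125, 0.25, 0.375, 0.5 SD over four visits. The slope on each earlier visit is ρ/(1 + 2ρ), so the imputed 3/7 carry an effect of 0.75ρ/(1 + 2ρ).
- ρ = 0.4: 0.571 × 0.5 + 0.429 × 0.167 = 0.36 SD.
- ρ = 0.7: 0.571 × 0.5 + 0.429 × 0.219 = 0.38 SD.

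A separate check with a true 0.5 SD effect building over visits gave about 0.37–0.39 SD, and adding arm restored 0.50 SD.

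**7. Who counts as observed.** The Analysis Plan defines the outcome by TLFB, while the complete-case model also excludes people for missing urine THC. The data-management text collects recalled Week 4 use by phone or email and flags it, but does not say whether it counts as measured.

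**The case against.** The restriction is not hidden. It stands in the same sentence as the label, the label follows the words about taking treatment, and the sentence points ahead to missed visits. All of that is true. It makes the set clear, but does not make it the set the label names.

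A reader might infer that the plan ignores people lost to follow-up. It does not: it imputes them, compares missingness by arm, attempts recall of Week 4 use and has retention steps. None of these chooses a lead estimate.

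A reader might also infer eight rival results and an inflated false-positive rate. The documents do not support this. Male and female effects are separate questions. The adjusted model by sex is inferred from a general sentence, and only the unadjusted model is written under Hypothesis 1a; if that is taken to lead, two estimates compete rather than four. No alpha is stated and the aim is estimation. At an assumed 0.05, the simulation in step 3 gave about a 15% chance that at least one of eight results is significant under no effect, against about 5% for one. That is illustrative only, and naming one result per sex would still leave about 1 − 0.95² = 9.75%.

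The best objection concerns the remedy. Promoting the imputed model as written could shrink the effect the pilot is meant to estimate (step 6), and even a better-specified one does not remove bias from outcome-related loss (step 5). This stands, and it changes the fix.

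**Conclusion.** The point holds as a fault of labelling and ordering. The set called intent-to-treat lacks a property the term claims, and the primary analysis has no lead among up to four estimates within each sex. The share left out is anywhere up to 43%, depending on when the loss occurs.

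The documents do not show that the observed-outcome estimate is biased. The 0.21–0.34 SD shift rests on one-sided, outcome-related loss, which is assumed. Nor do they make imputation right by default: as specified it may reduce a 0.5 SD effect to roughly 0.36–0.39 SD under the stated assumptions. The spread between versions is also simulated, but a median of 0.35 SD is close to the 0.45 SD standard error within a sex. The choice of version therefore matters for the figure this pilot passes on. The correction should be made before the analysis.

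**What to change.** - **Analysis Plan:** relabel the set as participants with an observed Week 4 outcome, by assigned arm. Reserve intent-to-treat for an analysis of all randomized. State whether a missing urine THC alone excludes someone and whether recalled Week 4 use counts as observed.
- **Hypothesis 1a and missing data plan:** name one lead estimate (one missing-data model, one adjustment version) before unblinding, and mark the others as supportive. The Statistical Analysis Core holds assignments from Baseline, so in practice this means before it looks at outcomes by arm. If an adjusted version leads, close the covariate list.
- **If the all-randomized imputed model leads:** include treatment arm, sex and baseline use in the imputation model as well as earlier TLFB and THC. Let the arm effect differ by sex, since the effect is estimated by sex. Keep the complete-case result as a sensitivity analysis.
- **Reporting:** give numbers randomized and analysed, by arm and sex, beside each estimate. Omit significance-based multiplicity figures or mark them as illustrative.

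No new data or participants are needed, and every type of model is already planned. The cost is plan text and, if imputation leads, respecifying that model. The headline interval would then depend on the imputation model, and bias from outcome-related loss would be reduced but not removed.

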Marijuana abuse is growing in the age group we are studying (20-60 years) and may continue to increase as other states in addition to Washington and Colorado legalize marijuana. There is a high rate of co-use with nicotine and given we are successfully recruiting nicotine dependent subjects we feel that we have an exceptional opportunity to capture this comorbid population and examine effects of progesterone treatment for cessation of marijuana.

Specific Aims

This study will be similar to the ongoing double-blind clinical trial of Progesterone (PRO) vs. placebo (PBO) for cigarette smoking cessation which is successfully being conducted (currently in year 4 of 5). We will enroll a parallel participant group of marijuana smokers who are co-using nicotine cigarettes, randomized 1:1 to PRO vs. PBO in a pilot double-blind trial, adjusting the protocol to address our time constraints. Our aims are:

Primary Aim: To estimate the association between PRO vs. PBO and percent reduction of marijuana use in

males and females who are co-users of cigarettes.

Hypothesis 1a. Males and females randomized to exogenous PRO will have greater percent reduction in marijuana use compared to those randomized to placebo.

Hypothesis 1b. Males compared to females, regardless of randomization, will have greater percent reduction of marijuana use.

Hypothesis 1c. Males and females, regardless of randomization, with higher levels of serum progesterone, will have a greater percent reduction in marijuana use.

Exploratory Aim: To estimate the association between impulsivity and percent reduction in marijuana use in males and females who are co-users of cigarettes.

Hypothesis 2a. Males and females with lower impulsivity at baseline will have greater reductions in marijuana use.

Hypothesis 2b. Higher serum levels of progesterone in males and females are predicted to reduce impulsivity and marijuana use.

Methods

Study Design, Recruitment and Subject Sample

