- *Behavioral Inhibition/Activation scales (BIS/BAS)*: 20-item form is commonly used to study externalizing tendencies (Carver and White, 1994). Investigators in Project II have used this instrument with success.
- *Barratt Impulsiveness Scale (BIS)*: 30-item self-report measure of self-control (Patton et al 1995). Doran and colleagues (2004) demonstrated that impulsivity, as measured with this item, was a predictor of smoking relapse.
- *Brief Self Control Scale (BSCS)*: This item consists of 13 questions rated on a 4-point scale from “very true” to “very false” on items reflecting the ability to control problematic behaviors (Tangney et al 2004).

The *Impulsivity Tasks* represent two forms of impulsivity, 1) impaired cognitive inhibitory mechanisms, and 2)

deficits in motor inhibitory mechanisms. “Delay discounting” entails higher-level cognitive inhibitory processes that may characterize the behavior of individuals who are drug dependent (Bickel and Marsch, 2001) tobacco users (Baker et al. 2003), cocaine users (Monterosso et al, 2001), other drug users (e.g. Vuchinich and Simpson, 1998; Kollins, 2003) and pathological gamblers (Dixon et al, 2003). The following items will be completed at Screening Visit 2 and Week 4.

- **Delay Discounting Task:** Developed by de Wit and colleagues (Richards et al, 1999), delay discounting refers to the reduction in value of a reward over time relative to its immediate worth. One’s discount rate, also known as a time preference, is a measurable individual difference and involves a series of choices (e.g. Petry and Casarella, 1999): one option is an immediate payment (e.g. \$1); the second option is a larger payment (e.g. \$50) after a delay (e.g. 6 hours to 25 years). Titrating the payment amounts at each delay interval allows the identification of points of indifference (the point at which the subject switches from choosing the immediate to the larger reward at a given delay interval). We additionally included a probability discounting condition to measure risk aversion in addition to time preference (Richards et al, 1999).

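### Hypothesis 1a covers both sexes together, but its only written model is fitted within each sex, and no pooled treatment coefficient is named as the overall effect

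*Combined protocol and SAP*

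**What the plan says.** Specific Aims states Hypothesis 1a as one claim about both sexes: "Males and females randomized to exogenous PRO will have greater percent reduction in marijuana use compared to those randomized to placebo". The Primary Aim is framed in the same way.

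The Analysis Plan says that "the intent of these analyses is to estimate magnitude and direction of treatment effects and associations with impulsivity (sex-specific and overall"; the Power paragraph repeats this: "This study will estimate magnitude and direction of treatment effects and associations with impulsivity (sex-specific and overall".

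Under Addressing Hypothesis 1a, the only model is an unadjusted "linear model of percent reduction in marijuana use on randomized treatment assignment, separately by sex". Hypotheses 1b, 1c, 2a and 2b each have a model that includes both sexes. For 1b: "A linear model including both males and females will be used to estimate the overall gender effect on percent reduction in marijuana use".

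On adjustment, the Analysis Plan says that "both unadjusted and adjusted assessments of effects will be carried out by including the randomized treatment assignment". The other terms in these models are described as "pre-specified adjusting covariates such as age, baseline progesterone, estradiol", plus baseline impulsivity measures and an open-ended remainder. The list is to be settled before the first enrollment. Sex is not among the covariates named, although it is the randomization stratum (Baseline Visit). The Missing data plan runs the primary analysis twice, once excluding participants without week 4 data and once with multiple imputation. It does not say whether either version is pooled or by sex.

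**The concern.** The pilot exists to estimate the size and direction of the PRO effect for a later trial. Its primary randomized hypothesis spans both sexes, yet the plan followed literally answers it with two separate comparisons of about 10 v 10. The other four hypotheses, none of which targets the randomized contrast, do get a model with everyone in it.

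Three matters are therefore left to be settled after the data are seen: whether an overall estimate is reported, how it weights the two sexes, and whether the adjusted and imputed versions are pooled or by sex.

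**Working it through.** **Text check.** Each place that could define an overall PRO v PBO estimate:

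| Place | Both sexes in one model? | Target |
|---|---|---|
| Hypothesis 1a model | No, by sex | Treatment effect, unadjusted |
| Hypothesis 1b model | Yes | Sex effect; no treatment term named |
| Hypothesis 1c model | Yes | Serum progesterone |
| Hypothesis 2a model | Yes | Impulsivity |
| Hypothesis 2b model | Yes | Impulsivity by progesterone |
| General sentence on adjustment | Not stated | Treatment plus covariates |
| Missing data plan | Not stated | Primary outcome analysis, two versions |

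No row both pools the sexes and targets the treatment effect, and no rule is given for combining the two by-sex estimates.

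**Inputs for the size.** Study Design plans 20 completers per drug group, half female, so 10 per sex-by-arm cell. The plan gives no SD, effect size or power calculation, so there is no stated figure to reproduce. I assume a common outcome SD of 1 and two-sided 95% intervals.

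**Formula.** SE = SD × sqrt(2 / n per arm); half-width = t(0.975, df) × SE.

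- Within a sex: SE = sqrt(2/10) = 0.447; df = 20 − 2 = 18; t = 2.101; half-width = 0.94 SD.
- One model with treatment and sex: SE = sqrt(2/20) = 0.316; df = 40 − 3 = 37; t = 2.026; half-width = 0.64 SD.
- Ratio: 0.940 / 0.641 = 1.47.

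If all 70 enrolled gave an outcome, the half-widths would be 0.69 SD within a sex (17 and 18 per arm, df 33) and 0.48 SD pooled (35 per arm, df 67).

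**Unequal effects.** Suppose the effects are 0.8 SD in one sex and 0.2 SD in the other (illustration). The pooled model then estimates their average, 0.5 SD. The omitted interaction raises the residual variance to 1 + 0.15² × 40/37 = 1.024, and the half-width becomes 0.641 × sqrt(1.024) = 0.65 SD.

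**Weights.** With n1 and n0 participants per arm, the pooled coefficient weights each sex by n1 × n0 / (n1 + n0).

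- 10/10 in both sexes: 100/20 = 5 and 5, so equal weights.
- 10/10 in one sex and 5/15 in the other: 5 and 75/20 = 3.75. The weights are 5/8.75 = 57% and 43%, although each sex still has 20 completers.

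**The case against.** The strongest reply is that the plan nearly contains the missing model. The general sentence says assessments will include the randomized assignment, and the 1b model holds both sexes; adding treatment to 1b gives exactly a treatment-plus-sex model. But no sentence says this will be done, 1b targets the sex contrast regardless of arm, and nothing labels the resulting coefficient as the 1a effect. The phrase about sex-specific and overall estimation could also attach only to impulsivity. Hypothesis 1a covers both sexes either way.

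By-sex analysis is also a sound choice here. The parent programme studies sex differences, and randomization uses one table per sex. The expected serum progesterone contrasts differ as well (females 9-13 v 1-14 ng/mL, males 6-7 v 0-1 ng/mL). This stands, and is why the by-sex fits should stay.

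Three stronger readings are tempting but not supported:

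- *A reader might infer that precision is lost or the overall effect is unobtainable.* At 10 per cell the pooled estimate is the mean of the two by-sex estimates, with SE = sqrt(0.447² + 0.447²) / 2 = 0.316. The figures 0.94 and 0.64 describe different estimands.
- *A reader might infer that no adjusted analysis is planned.* One is promised; only its structure is unstated.
- *A reader might infer that many covariates will be fitted to about 20 people of one sex.* The by-sex wording is attached only to the unadjusted assessment, and the covariate list is open-ended with no count. Any adjusted half-width is therefore hypothetical, and none is relied on here. Because the list is to be fixed before enrollment, covariate choice is not the issue.

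**Conclusion.** The gap is real and should be fixed, but it is bounded. The plan names no overall estimate for its primary randomized hypothesis and leaves the structure of the adjusted and imputed versions open. The by-sex estimates it does define remain valid.

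The size, 0.64 SD for an overall effect beside 0.94 SD for each sex-specific effect, rests on 40 completers in four equal cells and a common SD, neither guaranteed. Enrolling 70 to obtain 40 allows for 1 − 40/70 = 43% loss, so uneven cells are plausible. In that case the pooled coefficient is no longer the simple average of the two sexes, and the choice of weights becomes a real one. The absence of a power calculation is not a fault in an estimation pilot and plays no part in this conclusion.

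**What to change.** Add to the Analysis Plan, before the data are examined:

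1. The overall Hypothesis 1a effect is the treatment coefficient, with its 95% CI, from one linear model in all evaluable participants with treatment and sex (the randomization stratum).
2. The adjusted model adds the pre-specified covariates to this same structure.
3. The complete-case and multiple-imputation versions of the primary analysis both use it.
4. The coefficient weights each sex by n1 × n0 / (n1 + n0). It equals the equal-weight average only when this quantity is the same in both sexes.
5. The separate by-sex fits stay as written and are reported beside the overall estimate.

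This changes wording only and needs no new data or visits. The pooled effect averages over sexes with different expected progesterone contrasts, so it cannot replace the by-sex estimates. It also assumes a common residual variance, unless a robust SE is used, and the adjusted version assumes common covariate slopes in both sexes.
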